30. MRZ. 2023

PROTOCOL SYNOPSIS

Open-Label Pilot Trial to Evaluate the Effects of Ilofotase Alfa on Biomarkers in Adult Patients with Hypophosphatasia

Title (short)

Pilot trial of single dose ilofotase alfa in hypophosphatasia

Trial code

Sponsor code: AP-recAP-HPP-01-01

Sponsor

AM-Pharma BV
[name]
The Netherlands

Trial center

Clinical Osteology and Clinical Trial Unit
Konig Ludwig Haus
[name]
[name]
Germany

Objectives

Primary objective:

- The change in Inorganic Pyrophosphate (PPi), and Pyridoxal 5'-phosphate (PLP) levels after low, and high dose ilofotase alfa in adult hypophosphatasia (HPP) patients.

Exploratory objectives:

- To determine the safety and pharmacokinetic (PK) profile of a single iv dose of ilofotase alfa in adult HPP patients.
- To determine the pharmacodynamic (PD) profile of a single iv dose of ilofotase alfa in adult HPP patients.

Design and Treatments

This is a single-center, open-label, randomized, parallel group clinical trial in adult patients with HPP. Two different dose levels (0.8 mg/kg and 3.2 mg/kg) will be assessed. Up to twelve patients will be randomized, 6 patients to each trial arm. Patients will receive a single dose of 0.8 mg/kg or a single dose of 3.2 mg/kg. Ilofotase alfa will be administered as a 1-hour iv infusion on day 1.

Trial period

The trial period will include a run-in period of 2 days (day -2 to day -1) before administration of ilofotase alfa (day 1), followed by 9 days of observation after the ilofotase alfa administration (day 2 to day 10), with an additional follow-up assessment 14 days after ilofotase alfa administration (day 15).

Patients

Up to twelve (12) patients \geq 18 years and \leq 85 years of age with HPP.

Inclusion criteria

At screening, the following inclusion criteria must be met:

1. 18-85 years old, inclusive.
2. Genetically confirmed variant in the tissue-nonspecific isozyme alkaline phosphatase (ALPL)-Gene.
3. Clinical symptoms of HPP.
4. Medical history with 1) at least two independent measures of Alkaline Phosphatase (ALP) below lower level of normal (LLN) and 2) at least one measurement of either PPi or PLP above upper level of normal (ULN).
5. Provision of signed and dated informed consent form (ICF) in accordance with local regulations at screening.
6. Patients must agree not to get pregnant/not to get their partner pregnant, during the trial:

- Women of Child Bearing Potential must agree to use adequate and effective contraception means (criteria CTFG, 2020) for the period between trial drug administration and 14 days thereafter.
- Post-menopausal females not requiring hormonal contraception are defined as: no menses for 12 months without an alternative cause, and follicle stimulating hormone level must be used to confirm post-menopausal state in women not using hormonal contraception or hormonal replacement therapy (CTFG, 2020).
- Male subjects must agree to wear a condom during sexual intercourse and in case their partner is of child bearing potential they must agree to use adequate and effective contraception means (criteria CTFG, 2020) for the period between trial drug administration and 14 days thereafter.

Exclusion criteria

A patient who meets any of the following exclusion criteria at screening and/or baseline is excluded from participation in this trial:

1. Is unable or unwilling to participate in all scheduled visits and perform all protocol-mandated assessments.
2. Has a known or suspected hypersensitivity to ilofotase alfa or any components of the formulation used.
3. Body weight < 40 kilogram and > 120 kilogram.
4. Patient has a history of clinically significant abnormalities or of any illness that, in the opinion of the trial investigator, might confound the results of the trial or pose an additional risk to the patient by their participation in the trial.
5. NSAID use in the past 2 weeks.
6. Use of corticosteroids in the past 4 weeks.
7. Use of compounds intended to interfere with bone metabolism (e.g. Denosumab, Teriparatide, Romosozumab, Raloxifene) in the past 3 months.
8. Use of bisphosphonates in the past 2 years.
9. Participation in a drug trial within 60 days, or five times the half-life of the drug, whichever is longer, prior to administration of ilofotase alfa.
10. Use of asfotase alfa in the previous 3 months. Patients will not be withheld from approved asfotase alfa if medically indicated.
11. A patient who is currently pregnant or lactating.
12. Use of supplements including Vitamin B6.

Trial Drug, Dosage, and Route of Administration

Trial drug (ilofotase alfa) is provided in glass vials as a concentrate for infusion (aqueous buffer at a pH of 7.0). Prior to administration, the trial drug will be diluted with sterile sodium chloride 0.9% for injection (isotonic saline), United States Pharmacopeia (USP) / European Pharmacopoeia (EP) or equivalent, to a final volume of 50 mL and administered as an iv infusion using a dosing syringe. Trial drug will be administered as a 1-hour continuous iv infusion via a peripheral access point.

Prohibited Medication during the trial period

1. NSAIDs
2. Corticosteroids
3. Compounds intended to interfere with bone metabolism (e.g. Denosumab, Teriparatide, Romosozumab, Raloxifene)
4. Bisphosphonates
5. Supplements including Vitamin B6
6. Asfotase alfa

If there is a clinical indication to start any of these above medication, the subject should be withdrawn from the trial. Subjects who initiate any of the medication mentioned above during the trial period will be considered dropouts.

Criteria for evaluation

Primary endpoints

PPi and PLP serum concentration levels – recorded on day 1 (post dose) trough day 10 (inclusive).

A composite endpoint of the lowest serum concentration level of each of PPi and PLP will be created.

Exploratory endpoints

Pharmacokinetics: ilofotase alfa serum concentrations measured between day 1 and day 10 (inclusive).

Safety: Adverse events (AE) measured between day 1 and day 15 (inclusive).

	Vital signs (including supine systolic and diastolic blood pressure, pulse, body temperature, respiratory rate) measured at screening, on day 1, and on day 10.
	Clinical laboratory (including clinical chemistry, hematology, and urinalysis) tests, physical examination measured on day 1 and day 10 and listed in footnotes 6 and 7 of Table 1.
	Presence of anti-ilofotase antibodies detected on day 10.
Pharmacodynamics	Urine phosphoethanolamine (PEA) - measured between day 1 and day 10 (inclusive). Immediately consecutive sampling (second morning urine) of urine and blood for creatinine, phosphorus, and calcium concentrations to assess phosphate reabsorption (ratio of tubular maximum reabsorption of phosphate (TmP) to glomerular filtration rate (GFR)(TmP/GFR) and tubular reabsorption of phosphate (TRP)) kidney function and Ca/creatinine ratio. Blood samples for: Purines, 25 OH Vitamin D, alkaline phosphatase (ALP) activity and Isoenzymes, c-Terminal Fibroblast Growth Factor-23 (iFGF-23), parathyroid hormone (PTH), C-terminal telopeptide (CTX), procollagen type I N-propeptide (PINP), Osteocalcin, Vitamin B6 VitamerPL, phosphoethanolamine (PEA) in Urine (absolute and relative to sCreat) D measured between day 1 and day 10 (inclusive).

Statistical methods

The final database lock (DBL) will take place after the final patient has reached day 15 and the final PPi and PLP levels have been reported.

Primary endpoint

This analysis will use the intention to treat (ITT) analysis set.

Biochemical markers of HPP (PPi, and PLP) will be recorded for each patient at baseline (days -2, -1 and 1 before randomization) and after treatment, starting on day 1 and ending on day 10. PPi, and PLP levels will be listed and summarized for each of day 1 to day 10, overall and by trial arm. The median (minimum, maximum), mean, standard deviation (SD) and standard error of the mean (SEM) PPi, and PLP levels will be described overall and by trial arm. These data will also be displayed graphically.

For both PPi, and PLP the mean change and percentage change from baseline (with SD) will be tabulated per study day and by trial arm and shown graphically. The baseline value will be defined as the median value of the measurements prior to randomization.

The maximum change and percentage from baseline (with SD) will be tabulated and shown graphically overall and by trial arm.

Exploratory endpoints.

Endpoints as listed under exploratory objectives will be listed and summarized, overall and by trial arm, using descriptive statistics by scheduled time point. No statistical tests will be performed on exploratory endpoints.

Safety

Safety will be assessed by examining the incidence of adverse events, serious adverse events and will be categorized by Medical Dictionary for Regulatory Activities (MedDRA) System Organ Class (SOC) and Preferred Term (PT) and will be summarized by trial arm and overall. Physical examination findings will be reported by trial arm and overall using the safety analysis set (SAS). For adverse events, seriousness, severity, relationship to trial drug and whether leading to trial drug discontinuation or application of any emergency remedy will be displayed.

Anti-ilofotase alfa antibodies

Any patient who is found to have antibodies against ilofotase alfa measured at day 10 and showing an increase from baseline will be considered positive for antibodies. Tables showing the number (and percentage) of patients who were positive at baseline (by trial arm and overall) and who were positive by day 10 (by trial arm and overall) will be shown using the ITT analysis set. Also, a table showing the number of patients who became positive by day 10 having been negative at baseline will be shown (by trial arm and overall).

Table 1. Schedule of Assessments

Visit	Pre-Treatment		Treatment	Follow up									
	day -2	day -1		day 2	day 3	day 4	day 5	day 6	day 7	day 8	day 9	day 10 /early withdrawal ¹	day 15
Trial day			day 1 ¹⁰										
Informed consent	X												
Eligibility check ²	X		X										
Medical history	X												
Demographics	X												
Physical examination	X		X									X	
Body weight + height ³	X		X										
Pregnancy test ⁴	X		X										X
Defining FSH level ⁵	X												
Safety laboratory	X		X										X
12-lead ECG	X												
Vital signs	X		X										X
Randomization			X										
Trial drug administration			X										
PK			X ⁶	X	X	X	X	X	X	X	X	X	X
PPi, PLP ⁷	X	X	X ⁸	X	X	X	X	X	X	X	X	X	X
Urine samples ⁹	X	X	X	X	X	X	X	X	X	X	X	X	X
Exploratory biomarkers ¹⁰	X	X	X	X	X	X	X	X	X	X	X	X	X
ADA samples			X										X
Previous and concomitant medication	X		X	X	X	X	X	X	X	X	X	X	
AE monitoring ¹¹			X	X	X	X	X	X	X	X	X	X	X

¹ Women of child bearing potential having day 10 assessment done on their early withdrawal date will need to be tested for pregnancy

² Check against inclusion and exclusion parameters

³ Body weight and length will be used to calculate the body mass index (BMI), height only at screening

⁴ Only for women of childbearing potential

⁵ Only for postmenopausal women

⁶ PK sampling on day 1 will include baseline, end of infusion, 2, 4 and 8 hours post infusion

⁷ Samples to be drawn in the morning while fasting, for PPi and PLP (both Vitamers)

⁸ Samples at baseline, 2, 4 and 8 hours after start dosing will be in non-fasted patients

⁹ Immediately consecutive sampling (second morning urine) of urine and blood for PEA, creatinine, phosphorus, and calcium concentrations. To assess phosphate reabsorption (TmP/GFR and TRP) kidney function and Ca/creatinine ratio

¹⁰ 25 OH Vitamin D, ALP Isoenzyme, c-Terminal iFGF-23, PTH, CTX, PINP, Osteocalcin, PEA Urine (absolute und relative to sCreat), Purines and other biomarkers

¹¹ This includes SAE reporting

¹⁰ Baseline is defined as measurements taken on day -2, day -1 and day 1. Measurements taken on day 1 must be taken at any time up to immediately before randomization to be considered as baseline measurements. Measurements taken at or after randomization are not considered baseline measurements. Note that there is no day 0.

TABLE OF CONTENTS

1. INTRODUCTION	12
1.1 Background	12
1.1.1 Alkaline Phosphatase and Hypophosphatasia	12
1.1.2 Recombinant Human Alkaline Phosphatase (ilofotase alfa)	12
1.1.3 Clinical Studies with Recombinant Human Alkaline Phosphatase (ilofotase alfa)	12
1.2 Rationale.....	12
Risk - Benefit	13
2. OBJECTIVES	13
3. INVESTIGATIONAL PLAN.....	13
3.1 Trial Design and Plan.....	13
3.1.1 Trial design.....	13
3.1.2 Screening and Informed consent.....	13
3.1.3 Treatment Period.....	13
3.1.4 Follow-up	13
3.1.5 Discussion Trial Design.....	13
3.2 Selection of Trial Population.....	14
3.2.1 Inclusion Criteria	14
3.2.2 Exclusion Criteria	14
3.2.3 Removal of Patients from Therapy or Assessment.....	15
3.3 Treatments.....	15
3.3.1 Treatments Administered	15
3.3.2 Identity of Investigational Product	15
3.3.3 Trial Drug Preparation	15
3.3.4 Trial Drug Administration.....	16
3.3.5 Trial Drug Handling and Storage	16
3.3.6 Drug accountability.....	16
3.3.7 Drug Storage	16
3.3.8 Method of Assigning Patients to Treatment Groups	16
3.3.9 Meals during the Trial	17
3.3.10 Blinding	17
3.3.11 Previous / Concomitant Medication and Other Restrictions during the Trial	17
3.3.12 Treatment Compliance	17
3.3.13 Prohibited Medication During the Trial (including the screening period)	17
3.3.14 Female subjects	17
3.4 Sample collection.....	18
3.4.1 Primary endpoint samples	18
3.4.1.1 PPi.....	18
3.4.1.2 PLP.....	18
3.4.2 Exploratory assessments	18

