3.3.9 Meals during the Trial

There are no special requirements related to food and beverage intake during the trial. Patients should abstain from alcohol from day -2 to day 10 of the trial.

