3.4.2 Exploratory assessments

Immediately consecutive sampling (second morning urine) of urine and blood for creatinine, phosphorus, and calcium concentrations to assess phosphate reabsorption (TmP/GFR and TRP) kidney function and Ca/creatinine ratio.

Blood samples for: 25 OH Vitamin D, ALP activity and Isoenzymes, iFGF-23, PTH, CTX, PINP, Osteocalcin, PL, and processed following the laboratory manual.

Blood sample for purine measurement processed following the laboratory manual.

For serum collection, blood samples will be allowed to clot for 30-60 minutes and then centrifuged for 15 min to separate the serum. For plasma sample collection, blood samples will be centrifuged within 15 minutes of collection to yield plasma. After collection of the serum/plasma in new tubes the samples will be stored at -80 °C until assessment.

Urine samples (for PEA, absolute and relative to Creatinine) will be collected as fresh as possible and transferred specimen from standard urine collection cup into the pre- labeled transfer tubes. After collection the urine samples will be stored at -80 °C until assessment.

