3.6.2.1 Primary endpoint

This analysis will use the intention to treat (ITT) analysis set.

Biochemical markers of HPP (PPI, and PLP) will be recorded for each patient at baseline (days -2, -1 and 1 before randomization) and after treatment, starting on day 1 and ending on day 10. PPI, and PLP levels will be listed and summarized for each of day 1 to day 10, overall and by trial arm. The median (minimum, maximum), mean, standard deviation (SD) and standard error of the mean (SEM) PPI, and PLP levels will be described overall and by trial arm. These data will also be displayed graphically.

For both PPI, and PLP the mean change and percentage change from baseline (with SD) will be tabulated per study day and by trial arm and shown graphically. The baseline value will be defined as the median value of the measurements prior to randomization.

The maximum change from baseline will be tabulated (median, minimum, maximum, mean (including SD, SEM and 95% confidence interval)) and shown graphically (mean, SD and 95% confidence interval) overall and by trial arm.

3.6.2.2 Exploratory endpoints.

Endpoints as listed under exploratory objectives will be listed and summarized, overall and by trial arm, using descriptive statistics by scheduled time point. No statistical tests will be performed on exploratory endpoints.

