3.6.3 Determination of Sample Size

No formal sample size calculation is provided as the purpose of this trial is exploratory. Up to twelve patients will be randomized, 6 to each trial arm. If this randomization rate is not achieved in a reasonable timeframe, the Sponsor will review the required sample size.

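### The creatinine denominator for urine PEA is undefined and named inconsistently; read literally as serum creatinine, it cannot correct a spot urine for dilution

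*Protocol*

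**What the plan says.** Three places describe the creatinine-related form of urine PEA.

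- Synopsis, criteria for evaluation, pharmacodynamics: "phosphoethanolamine (PEA) in Urine (absolute and relative to sCreat").
- Table 1, the footnote 10 attached to the exploratory biomarkers row: "PEA Urine (absolute und relative to sCreat").
- Section 3.4.2: "Urine samples (for PEA, absolute and relative to Creatinine"), with no prefix and no specimen named.

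The abbreviation sCreat is not in the list of abbreviations.

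The specimen is a spot urine. Table 1 footnote 9, on the urine row, describes it: "Immediately consecutive sampling (second morning urine) of urine and blood for PEA, creatinine, phosphorus, and calcium concentrations". Section 3.4.2 also has creatinine measured in the paired urine and blood: "Immediately consecutive sampling (second morning urine) of urine and blood for creatinine, phosphorus, and calcium concentrations to assess phosphate reabsorption". Both candidate denominators will therefore exist. On fluids, section 3.3.9 states: "There are no special requirements related to food and beverage intake during the trial".

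The endpoint is exploratory and is to be listed and summarized by time point. Section 3.6.2.2 adds: "No statistical tests will be performed on exploratory endpoints".

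**The concern.** A PEA concentration in a spot urine depends on how much PEA the patient excretes and on how dilute that void is. Dividing by creatinine is meant to remove the second part. It does so only if the denominator is diluted to the same degree, that is, if it is creatinine in the same urine. Serum creatinine is nearly constant from day to day within a patient and does not follow urine concentration. Dividing by it rescales the PEA value and corrects almost nothing.

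If the synopsis and Table 1 are followed literally, the report will carry a PEA value that looks corrected but is not. With 6 patients per arm summarized by time point, changes in hydration could hide or imitate a fall in PEA after dosing. Section 1.2 presents the trial as a pilot for a possible Phase 2/3 trial that looks at PPi, PLP and other biochemical markers, so the PEA profile may be carried forward.

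**Working it through.** The protocol gives no figure for this endpoint, so there is nothing to reproduce. The check has two parts.

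**1. What the denominator is.** The synopsis and Table 1 footnote 10 agree on sCreat. Section 3.4.2 has creatinine, in a sentence about urine samples. No place names urine creatinine as the PEA denominator, and none spells out serum. The term is undefined, and its ordinary meaning points one way while the context of section 3.4.2 points the other.

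**2. What each denominator does.** On the log scale, within a patient, let e be PEA excretion, d the dilution of the void, c creatinine excretion and s serum creatinine, taken as independent.

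- log urine PEA = e + d
- log urine creatinine = c + d
- log serum creatinine = s
- PEA over serum creatinine = e + d − s, with variance σe² + σd² + σs²
- PEA over urine creatinine = (e + d) − (c + d) = e − c, with variance σe² + σc²

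The coefficient on dilution is 1 with serum and 0 with urine creatinine. This holds whatever the standard deviations are.

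**Size.** All inputs are assumptions, since the protocol gives none: σe = 0.30, σd = 0.40 to 0.60, σs = 0.05, σc = 0.10 to 0.20. Coefficients of variation (CVs) are used as approximate log-scale standard deviations.

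Urine denominator: 0.30² + 0.10² = 0.1000 (CV 0.32), and 0.30² + 0.20² = 0.1300 (CV 0.36).

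| σd | Absolute PEA: 0.30² + σd² | Serum denominator: add 0.05² | Variance ratio, serum to urine, σc = 0.10 | σc = 0.20 |
|---|---|---|---|---|
| 0.40 | 0.2500 (CV 0.50) | 0.2525 (CV 0.50) | 2.5 | 1.9 |
| 0.50 | 0.3400 (CV 0.58) | 0.3425 (CV 0.59) | 3.4 | 2.6 |
| 0.60 | 0.4500 (CV 0.67) | 0.4525 (CV 0.67) | 4.5 | 3.5 |

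The serum ratio has practically the same spread as absolute PEA in every row. Its variance is about 1.9 to 4.5 times that of the urine ratio.

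**Sensitivity.** With σe = 0.20 and σd from 0.30 to 0.70:

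- Serum variance runs from 0.04 + 0.09 + 0.0025 = 0.1325 to 0.04 + 0.49 + 0.0025 = 0.5325.
- Urine variance is 0.04 + 0.01 = 0.05 or 0.04 + 0.04 = 0.08.
- The ratio then runs from 0.1325/0.08 = 1.7 to 0.5325/0.05 = 10.7.

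The direction is stable, but the size depends on the assumptions. Urine creatinine would lose its advantage only if σc² exceeded σd² + σs². At σd = 0.40 that means a creatinine-excretion CV above √0.1625, or about 40%.

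**The case against.** The strongest objection is that serum is an expansion of an undefined abbreviation. Section 3.4.2 refers to creatinine in a sentence about urine samples, where creatinine in that urine is the natural meaning, and the same paired sampling already feeds a calcium/creatinine ratio. Loose shorthand in the synopsis and a footnote is a plausible explanation. This stands. A reader might infer that the sponsor deliberately chose a serum denominator, and the protocol does not support that. It shows an undefined term in two places and an unspecified one in a third.

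A second objection is that the formula for a derived exploratory variable usually belongs in the SAP, which is not shown. That would answer a charge of missing detail. It does not fully answer this point, because the protocol does name a denominator, twice, and a later document using urine creatinine would depart from its literal wording.

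Third, little is at stake. PEA is one of many exploratory markers, no tests are planned on it, and section 3.6.3 says: "No formal sample size calculation is provided as the purpose of this trial is exploratory". Both creatinine values are collected, so the right ratio can be recovered. All of this stands. The one reservation is that choosing the denominator afterwards would be an unplanned decision on open-label data.

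Fourth, the second-morning specimen standardizes timing, so unrestricted drinking matters less than it might, and the assumed dilution range is not tied to that sampling scheme. This too is fair.

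**Conclusion.** The point holds as a wording defect with a real but limited consequence. The denominator for relative PEA is undefined and inconsistently named. Its literal reading in the synopsis and Table 1 gives a ratio with no dilution correction. That last statement is algebraic and needs only that serum creatinine does not move with urine dilution.

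The factor of about 1.9 to 4.5 in within-patient variance is illustrative and rests on the assumed CVs and on independence of the components. Two stronger figures are tempting. Treating urine creatinine as free of its own variation would give 0.2525/0.09 = 2.8 to 0.4525/0.09 = 5.0, but that credits only one denominator with noise. Dividing the within-patient CV by √6 would suggest that the standard error of an arm mean halves, but between-patient spread also enters a by-time-point arm mean, and the protocol gives no figure for it.

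Nor should a reader infer any effect on the primary analysis. PPi and PLP do not use this denominator.

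**What to change.** In the synopsis pharmacodynamics list, in Table 1 footnote 10 (exploratory biomarkers) and in section 3.4.2, state that PEA is given as absolute concentration and relative to urine creatinine in the same sample. Drop sCreat in the first two places. Keep absolute PEA listed and summarized as planned, since the defect gives no reason to demote it.

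The cost is one wording change in three places. Footnote 9 already has PEA and creatinine measured in the same second-morning urine, so no sample, assay or visit is added. If serum creatinine really was intended, the protocol should say so and give the reason, and the value should not be presented as corrected for dilution.
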